9.2 ANALYSIS OF EXPLORATORY ENDPOINTS

The analysis for the exploratory endpoints will be based on the FAS population.

9.2.1 Time to first RBC Transfusion

For a subject receiving a RBC transfusion, the Time at Risk (time up to first RBC transfusion) will be calculated (in weeks) as:

$$(\text{First RBC transfusion date} - \text{First dose date of study medication} + 1) / 7$$

For a subject not receiving a transfusion, the Time at Risk (time until they get censored) is calculated as:

$$(\text{Date of last study visit} - \text{First dose date of study medication} + 1) / 7$$

Subjects with no events were censored at the date of minimum (last dose date, last visit date, death date, Week 24*7).

Time to first RBC transfusion will be analyzed using the Kaplan-Meier method with KM curve plotted to derive the following:

- Proportion of subjects with any RBC transfusion up to Week 24

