4.6. Post-Treatment Follow-Up Period

After completing the Treatment Period (Week 24/EOT), subjects who wish to permanently discontinue roxadustat and switch to an ESA, the first ESA dose should be administered at least two days after the last roxadustat dose.

Subjects permanently discontinuing roxadustat, should have one final safety assessment 28 days after the last roxadustat dose.

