5.3. Subject Discontinuation and Withdrawal

The subject is free to permanently discontinue study medication at any time, without prejudice to further treatment. Discontinuation from study medication is not the same as complete withdrawal from the study (i.e., withdrawal of consent).

Protocol FGCL-4592-096 A01

Subjects may withdraw consent and discontinue from the study at any time by discontinuing study medication and refusing to return for any form of follow-up without any prejudice.

A subject who decides to discontinue study medication will always be asked about the reason(s) to discontinue study medication and the presence of AEs (if any). These data will be ascertained and documented by the investigator and recorded in the eCRF as appropriate. Any subject discontinuing study medication will be followed up for 28 days after discontinuing study medication whenever feasible for purposes of adverse event reporting.

Reasons for permanent discontinuation of study medication:

- Subject's decision (subject no longer wants to continue study medication (i.e., withdrawal of consent)
- Investigator's decision that it is in the best interest of the subject to be withdrawn from the study
- Adverse events
- Significant noncompliance with study procedures, as determined by Investigator or Sponsor
- Lack of efficacy / Meets ESA withdrawal criteria
- Subject is lost to follow-up
- Subject got transferred to a different location/dialysis center
- Subject is no longer requiring dialysis due to kidney transplant
- Site terminated by the sponsor
- Pregnancy
- Death

Upon discontinuation from the study, both female subjects of childbearing potential and male subjects with partners of childbearing potential must continue to use a medically acceptable method of contraception for 1 week following the last study drug administration.

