4.2 EXPLORATORY ENDPOINTS

- Proportion of subjects with a mean Hb level within 10-12 g/dL from Week 16 to Week 24
- Proportion of subjects with Hb > 12 g/dL any time during treatment
- Proportion of subjects with Hb > 13 g/dL any time during treatment
- Percentage of time with Hb, values within 10.0 to 12.0 g/dL from Week 16 to Week 24
- Time to first RBC transfusion
- Proportion of subjects with a mean Hb level ≥ 10 g/dL in the first 8 weeks after conversion or initiation of treatment
- Proportion of subjects with a mean Hb level ≥ 10 g/dL (averaged from Week 16 to Week 24) based on baseline ESA use status ≥ 6 weeks (conversion from ESA to roxadustat based on prior ESA use) and < 6 weeks (initiation of roxadustat based on body weight)
- Evaluate the utilization of IV iron (IV iron use/4 weeks)

- Evaluate the effect on iron indices
- Evaluate dosing adherence
- Conversion subjects: Comparison of starting dose of roxadustat to roxadustat dose at Weeks 16 to 24
- Mean number of dose adjustments (including dose-hold) during study
- Proportion of subjects requiring blood/pRBC transfusion from Week 5 (Day 29) to Week 24/ET.
- Proportion of subjects requiring rescue therapy (blood/pRBC transfusion or ESA rescue) from Week 5 (Day 29) to Week 24/ET

In addition to the exploratory endpoints in the protocol, additional exploratory efficacy endpoints of interest are presented in this section.

RBC transfusion data is collected in the Blood Transfusions form of the eCRF.

For efficacy evaluation, Hb values will be censored for 4 weeks if blood/pRBC is administered during the treatment period. Hb results obtained from the central laboratory will be used to determine the Hb response.

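### SAP 9.2.1 gives two conflicting censoring dates for time to first RBC transfusion; if the minimum rule is programmed with uncut events, the 24-week Kaplan-Meier proportion is biased upward

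*SAP*

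**What the plan says.** All of the following is in SAP 9.2.1 unless stated otherwise.

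- **Events.** "For a subject receiving a RBC transfusion, the Time at Risk (time up to first RBC transfusion) will be calculated (in weeks) as" the first transfusion date minus the first dose date plus 1, divided by 7. No limit at last dose is given.
- **Censoring, formula.** "For a subject not receiving a transfusion, the Time at Risk (time until they get censored) is calculated as" the same expression with "Date of last study visit" as the end date.
- **Censoring, next sentence.** "Subjects with no events were censored at the date of minimum (last dose date, last visit date, death date, Week 24*7").
- **Output.** A plotted Kaplan-Meier curve and, derived from it, the "Proportion of subjects with any RBC transfusion up to Week 24".

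Three other places bear on this.

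- Protocol 4.6: "Subjects permanently discontinuing roxadustat, should have one final safety assessment 28 days after the last roxadustat dose". Protocol 5.3 adds: "Any subject discontinuing study medication will be followed up for 28 days after discontinuing study medication whenever feasible".
- SAP 4.2: "RBC transfusion data is collected in the Blood Transfusions form of the eCRF". It sets no on-treatment restriction.
- SAP 9.2.8 limits a transfusion proportion to Day 29 through Week 24/ET. That is a separate endpoint and does not govern 9.2.1.

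**The concern.** The two end dates are different dates for anyone who stops drug early and attends the 28-day assessment, and nothing in either document says which one governs. Two programmers could follow the SAP faithfully and produce different curves.

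The minimum rule has a further fault. It cuts untransfused subjects at last dose but does not cut events there. Whether an early stopper stays in the risk set after last dose then depends on whether that subject is later transfused. This is outcome-dependent censoring. It shrinks the denominator but keeps the events, so the Kaplan-Meier risk goes up.

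The result matters to the extent that Protocol 2.7 names a reduced risk of transfusion as part of the drug's primary benefit. Protocol 5.3 lists lack of efficacy among the reasons for stopping, so transfusions soon after stopping are plausible.

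**Working it through.** The plan states no event rate or precision for this endpoint, so there is no figure of its own to reproduce. Three rules are compared:

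- **A**: every captured transfusion is an event; others are censored at last visit (the SAP formula).
- **B**: every captured transfusion is an event; others are censored at min(last dose, last visit, death, Day 168) (the SAP sentence, read literally; 24*7 = 168).
- **C**: events and censoring are both cut at the minimum in B (a matched on-treatment version, not in the SAP).

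**Hand example (assumed counts).** N = 300. Of these, 24 are transfused on treatment before Day 84. Another 60 stop at Day 84 and are followed to Day 112, and 4 of the 60 are transfused at Day 98. The other 300 - 24 - 60 = 216 complete.

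- After the first 24 events, survival is 276/300 under every rule.
- A: all 60 stoppers are still at risk at Day 98, so the risk set is 216 + 60 = 276. Risk = 1 - (276/300)(272/276) = 9.33%.
- B: the 56 untransfused stoppers left at Day 84, so the risk set is 216 + 4 = 220. Risk = 1 - (276/300)(216/220) = 9.67%.
- C: the 4 later transfusions fall outside the window. Risk = 1 - 276/300 = 8.00%.

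A and B count the same 28 events. The gap of 0.34 point comes only from the risk set.

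**Simulation.** Daily Kaplan-Meier at Day 168, with 400,000 subjects per scenario. These inputs are assumptions, not taken from the documents: 24-week on-treatment risk 5, 10 or 17%; early stopping 0, 10, 20 or 30%; transfusion hazard after stopping 1 or 3 times the on-treatment hazard; deaths 3%. Transfusions are taken as captured for 28 days after last dose, in line with Protocol 4.6 and 5.3. The 17% value was chosen in view of the hemodialysis transfusion rates of 2.7% to 3.8% in Protocol 2.2. Their period is not stated; if they are monthly, 1 - (1 - 0.027)^(168/30.4) = 14.0% and 1 - (1 - 0.038)^(168/30.4) = 19.3%.

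| Risk | Stopping | Hazard after stop | A % | B % | C % | B - A | A - C |
|---|---|---|---|---|---|---|---|
| 10% | 0% | n/a | 9.98 | 9.98 | 9.98 | 0.00 | 0.00 |
| 5% | 10% | 1x | 4.94 | 5.02 | 4.94 | 0.08 | 0.00 |
| 10% | 20% | 1x | 10.01 | 10.34 | 10.03 | 0.33 | -0.02 |
| 10% | 20% | 3x | 10.56 | 10.89 | 9.94 | 0.33 | 0.62 |
| 17% | 30% | 1x | 17.01 | 17.86 | 17.04 | 0.85 | -0.03 |
| 17% | 30% | 3x | 18.49 | 19.35 | 16.86 | 0.86 | 1.63 |

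B - A is the effect of mismatched censoring. Across all scenarios with 10-30% stopping it ran from 0.08 to 0.86 point, and it hardly changed with the hazard after stopping. With no early stopping it was zero. At 1x hazard, A recovers the assumed risk to within simulation error and B does not, so B is the biased rule.

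A - C is a different quantity: the effect of counting transfusions after last dose at all.

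**Scale.** For 300 subjects, 0.86 point is 0.0086 x 300 = 2.6 subjects. The half-width of a normal-approximation 95% interval at 10% risk is 1.96 x sqrt(0.1 x 0.9/300) = 3.4 points.

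**The case against.** The strongest objection is that the bias is conditional. It needs three things together: the minimum rule is the one programmed, some subjects stop early, and some of them have a recorded transfusion after last dose but by Week 24. Under the last-visit formula in the same section, events and risk set cover the same follow-up and the mismatch does not arise. This stands. A reader might infer from the text that the reported 24-week risk will be overstated. The documents do not support that, because they leave open which rule governs.

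A reader might also take the whole distance from B to C, up to about 2.5 points in these scenarios, as the error. That does not follow either. The SAP never says this endpoint is on-treatment only, and SAP 9.2 analyses it in the FAS. In the last row of the table, 1.63 of that distance is a choice of estimand and only 0.86 is mismatched censoring. The stopping rates and hazards are assumed as well. Protocol 4.6 allows an ESA from two days after the last dose, so a much higher hazard after stopping is not self-evident.

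Nor does the missing Week 24 limit on events inflate the Week 24 figure, since Kaplan-Meier at Week 24 ignores later event times. If anything, an early stopper transfused after Week 24 stays in the risk set longer and lowers it slightly. The missing limit matters only for a curve plotted past Day 168: under the minimum rule the risk set there would contain only subjects with events.

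Finally, the stakes are low. The endpoint is exploratory, SAP section 11 states that no hypothesis is tested, and SAP 9.2.8 reports a crude transfusion proportion separately. This limits the importance of the point but does not settle which date applies.

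**Conclusion.** The conflict between the two censoring dates is plain on the page, and no other section resolves it. If the minimum rule is programmed with uncut events, the 24-week proportion is biased upward. Relative to the last-visit rule the size is about 0.1 to 0.9 point, on assumed stopping of 10-30%, 24-week risks of 5-17% and capture of transfusions for 28 days after last dose. It is zero without early discontinuation. The direction is certain under those conditions; the size in this trial cannot be known from the documents. The effect is small beside the sampling error, but it is systematic and the remedy costs almost nothing, so the SAP should be corrected.

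**What to change.** Define one end-of-observation date per subject in SAP 9.2.1. Count a first transfusion as an event only if it falls on or before that date, censor everyone else at that date, and delete the other rule. Either of these removes the mismatch:

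- min(last visit, death, Week 24), if the estimand includes follow-up after stopping; or
- min(last dose plus a stated lag, death, Week 24), if the estimand is on-treatment. In this version no subject should be held at risk beyond the last contact.

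The SAP should say which estimand is meant. The on-treatment version with a short lag can miss transfusions linked to treatment failure, because lack of efficacy is a listed reason for stopping, so the choice deserves a sentence of justification. Week 24 should be given as a day number: the censoring sentence implies Day 168, while SAP 13.2.1 schedules the visit on 7*24 + 1 = Day 169. Transfusions outside the window should be listed.

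The cost is a short change to the SAP text and about one line of code, with no new data.

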9.2.2 Hb Level

- Proportion of subjects with a mean Hb level ≥ 10 g/dL in the first 8 weeks after conversion or initiation of treatment
- Proportion of patient with a mean Hb level ≥ 10 g/dL (averaged from Week 16 to Week 24) based on baseline ESA use status ≥ 6 weeks (conversion from ESA to roxadustat based on prior ESA use) and < 6 weeks (initiation of roxadustat based on body weight)

For the Hb level exploratory analysis above, a MI method will be used. The imputation data will be generated in a method similar to the one described in [section 9.1.1](#). Similarly, the Rubin's method will then be used to combine the estimates of the proportion of responders and standard errors from each of the PROC FREQ procedure.

- Proportion of subjects with a mean Hb within 10-12 g/dL from Week 16 to Week 24
- Proportion of subjects with Hb > 12 g/dL any time during treatment
- Proportion of subjects with Hb > 13 g/dL any time during treatment
- Percentage of time with Hb values within 10.0 to 12.0 g/dL from Week 16 to Week 24

For the Hb level exploratory analysis above, observed Hb values will be used.

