2 STUDY DESIGN

[figure not shown]
This open-label single arm study is designed to evaluate roxadustat in maintaining hemoglobin (Hb) in ESRD subjects receiving in-center hemodialysis either after conversion from a stable ESA dose: ESA use \geq 6 weeks prior to conversion to roxadustat dosing or as initial anemia treatment, in subjects with < 6 weeks of total ESA use prior to start of roxadustat dosing.

The study periods are as follows:

- **Screening Period:** Up to 6 weeks
- **Treatment Period:** 24 weeks
- **Post-Treatment Follow-Up Period:** Subjects permanently discontinuing roxadustat, should have one final safety assessment (Treatment Emergent Adverse Events (TEAEs) and Treatment Emergent Serious Adverse Events (TESAEs)) 28 days after the last roxadustat dose.

An extension of roxadustat treatment after 24 weeks may be offered to interested subjects within the context of the study protocol upon agreement with the study site. Data listings for the extension phase will be generated upon database lock and will include serious adverse events (SAEs), concomitant medications related to SAEs, and hospitalization records related to SAEs.

Study Design Overview

Primary Efficacy Endpoint: • Proportion of subjects with mean Hb \geq 10.0 g/dL, averaged over weeks 16-24

Secondary Efficacy Endpoints: • Proportion of subjects with mean Hb between 10-12 g/dL, averaged from week 16 through week 24

Conversion subjects:

- Mean Hb change from baseline to average Hb from week 16-24

Subjects will be dosed three times weekly (TIW), except if a subject requires < 60 mg/week to maintain Hb levels, in which case dose frequency may be reduced in a stepwise fashion, e.g., to twice weekly (BIW), then once weekly (QW).

Initial Dose

Conversion from ESA to Roxadustat

The initial roxadustat dose is determined using a conversion table based on the subject's previous prescribed ESA dose in the last 4 weeks prior to enrollment (for Mircera®:in the last 8 weeks prior to enrollment) (Table 1.1).

Roxadustat treatment should start after the following intervals:

- Two days after stopping epoetin
- One week after stopping darbepoetin alfa
- Two weeks after stopping methoxy polyethylene glycol-epoetin beta (Mircera®)

If the converted initial dose exceeds the maximum dose of 3.0 mg/kg/dose then the next-lower dose step should be chosen as the initial dose.

Table 1.1. Conversion from ESA to Roxadustat

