5.3.2 Full Analysis Set (FAS)

The FAS set will consist of all subjects who signed the informed consent, were enrolled, and provided baseline Hb data and data for at least one post baseline Hb time point. The FAS set will be used for all efficacy endpoints.

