9 EFFICACY ANALYSES

Efficacy analysis will be conducted on the FAS population.

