9.1 ANALYSIS OF EFFICACY ENDPOINTS

9.1.1 Proportion of subjects with mean Hb ≥ 10 g/dL, averaged from Week 16 to Week 24

The efficacy endpoint will be evaluated using the proportion (%) of subjects with mean value of Hb measurements from Week 16 to Week 24 ≥ 10 g/dL.

Proportion of responders will be presented descriptively with counts and percentages and a 95% confidence interval of the responder rate. The 95% CI of the response rate will be presented based on normal approximation.

For the Hb efficacy analysis, a multiple imputation (MI) method will be used. This will be implemented on the raw Hb values, then the Hb-relates endpoint summaries will be derived based on the imputed data (algorithm as used for the previous phase 3 studies).

The following steps will be used to conduct the MI procedure of the Hb values:

1. Generate 200 datasets, using seed 12345, where only intermittent missing Hb data will be imputed relying on non-missing data from all subjects using the Monte Carlo Markov Chain (MCMC) imputation model using baseline Hb and the available non missing Hb for each scheduled week.

The MCMC statement in the SAS PROC MI procedure with monotone option will be used. As a result, each dataset will only have missing ending data, or a monotone missing data pattern.

2. For each dataset from step 1, missing ending data (Hb up through end of evaluation period) will be imputed. As a result, 200 imputed complete datasets will be generated.

- Missing data at Week 2 will be imputed using the regression imputation model with baseline and Hb from Week 2, using the SAS PROC MI procedure with the REGRESSION option in the MONOTONE statement.
- Repeat for all other scheduled weeks sequentially (Week 4 to the end of evaluation period). Subjects whose missing data were imputed for previous weeks will contribute to the imputation for the current week.
- The regression imputation model includes an intercept and the slopes of the Hb from previous weeks.

Steps 3 and 4 will be used to analyze proportion of subjects with a mean Hb level ≥ 10 g/dL, averaged from Week 16 to Week 24 using the imputed Hb data above:

3. Analyze each imputed complete dataset to estimate proportions of responders and their standard errors using the mean of all observed or imputed Hb values within the evaluation period (Weeks 16 to 24).

Sample SAS code:

```
PROC FREQ DATA=xx;
  TABLES resp_week16_24 / cl binomial (level=2);
  BY _Imputation_;
  ODS OUTPUT BINOMIALPROP=prop;
RUN;
```

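### The 10–12 g/dL proportion (SAP 9.2.2) uses observed Hb with no stated denominator, while the ≥10 g/dL proportion over the same weeks uses MI on the full FAS, so the two may not be directly comparable

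*SAP*

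**What the plan says.** **≥10 g/dL, Weeks 16–24.** SAP 9.1.1 states: "For the Hb efficacy analysis, a multiple imputation (MI) method will be used". Its second step says that "missing ending data (Hb up through end of evaluation period) will be imputed", and this yields 200 complete datasets. Each subject's Week 16–24 mean is then taken over observed and imputed values, and the 200 proportions are pooled with PROC MIANALYZE. In 9.2.2 the two exploratory ≥10 g/dL proportions (first 8 weeks, and Weeks 16–24 by prior ESA use) are treated the same way: "For the Hb level exploratory analysis above, a MI method will be used".

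**10–12 g/dL, Weeks 16–24.** The next block of 9.2.2 covers this proportion, the any-time >12 and >13 g/dL proportions, and the percentage of time in range. For all four: "For the Hb level exploratory analysis above, observed Hb values will be used".

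**Analysis set.** Both kinds of endpoint are assigned to the same set. SAP 9 says "Efficacy analysis will be conducted on the FAS population" and SAP 9.2 says "The analysis for the exploratory endpoints will be based on the FAS population". FAS membership requires that a subject "provided baseline Hb data and data for at least one post baseline Hb time point" (SAP 5.3.2). It does not require a value in Weeks 16–24.

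**Status of the endpoint.** The SAP Section 2 overview lists "Proportion of subjects with mean Hb between 10-12 g/dL, averaged from week 16 through week 24" as a secondary efficacy endpoint, whereas SAP 4.2 lists it as exploratory. It is not among the protocol's endpoints (Protocol 3.2).

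**The concern.** The two proportions cut the same quantity, the Week 16–24 mean Hb, at different values. A FAS subject who stops before Week 16 enters the ≥10 rate through imputation but has no observed mean for the 10–12 rate. The SAP does not say whether that subject leaves the 10–12 denominator or counts as a non-responder. It gives no reason for the split, and it plans neither an imputed 10–12 rate nor an observed-value ≥10 rate, so no planned output puts the two on one footing.

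The 10–12 rate is the only responder rate on mean Hb that matches the dosing target of 11±1 g/dL in the protocol synopsis; the ≥10 rate counts overshoot as success. No planned endpoint gives the share with a Week 16–24 mean above 12 g/dL, so the difference between the two rates is the natural way to obtain it.

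Missing Hb could plausibly depend on Hb. Lack of efficacy is a listed reason for stopping study drug (Protocol 5.3), and Hb is set aside for 4 weeks after a transfusion (SAP 4.2). Imputation can use such subjects' earlier Hb; the observed rate cannot. Protocol 9.3 also derives Hb-related summaries from imputed data in general, although it does not name this later-added endpoint.

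**Working it through.** **The plan's own figure, for scale.** The only responder-rate figure in the plan is a 95% CI width of 9.5% at 80% and N = 300. Clopper-Pearson on 240/300 gives 75.0% to 84.4%, a width of 9.36 points; exactly 9.5 needs about 291–292 subjects. The figure reproduces closely, and the present point does not depend on it.

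**Formulas.** Let m be the share of the FAS with no Week 16–24 Hb, p1 the 10–12 rate in subjects with data, and p0 the rate in those without.

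- Full-FAS rate: P = (1 − m)·p1 + m·p0
- Observed values, denominator = subjects with data: p1, with error p1 − P = m·(p1 − p0)
- Observed values, denominator = FAS: (1 − m)·p1, with error −m·p0
- Implied share above 12 = (≥10 rate) − (10–12 rate), taking the band as inclusive. If MI recovers the ≥10 rate, its error equals the error above with the sign reversed.

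The first error vanishes when m is small or p0 = p1. The second does not vanish when p0 = p1.

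**Inputs (all assumed; the documents give neither m nor p0).** 200,000 simulated subjects with Hb at the scheduled visits; mean rising from 10.3 at baseline to 10.9 at Weeks 16–24; SD 1.0; correlation 0.3 + 0.7·exp(−gap in weeks/8). Dropout occurs at Weeks 4, 6, 8 or 12, either unrelated to Hb or with log-odds rising by 1.0 for each g/dL by which the previous visit's Hb is lower. The full-data rates, which MI targets when dropout depends only on earlier observed Hb, are 84.6% for ≥10 and 74.1% for 10–12, so the true share above 12 is 84.6 − 74.1 = 10.5 points.

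| Dropout | Missing | 10–12, denominator with data | 10–12, denominator FAS | Implied >12 (with data) | Implied >12 (FAS) |
|---|---|---|---|---|---|
| Unrelated | 7.0% | 74.1% | 68.9% | 10.5 | 15.7 |
| Unrelated | 14.7% | 74.1% | 63.2% | 10.5 | 21.4 |
| Unrelated | 24.9% | 74.1% | 55.6% | 10.5 | 29.0 |
| Low Hb | 8.4% | 74.6% | 68.3% | 10.0 | 16.3 |
| Low Hb | 16.6% | 75.0% | 62.6% | 9.6 | 22.0 |
| Low Hb | 26.3% | 75.4% | 55.5% | 9.2 | 29.1 |

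The implied columns are 84.6 minus the 10–12 rate.

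**Last row by formula.** The error is 75.4 − 74.1 = 1.3 points, so p0 = 75.4 − 1.3/0.263 ≈ 70.5%. The implied share above 12 is 9.2 against 10.5, also 1.3 points off. With the FAS as denominator the 10–12 rate is 74.1 − 55.5 = 18.6 points too low.

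**A second simulation, with imputation run.** At 32% missing by Week 16 and Hb-dependent dropout, the true 10–12 rate was 76.0%, the observed-value rate 77.8% (+1.8) and the MI rate 75.9%. The MI ≥10 rate of 85.2% minus 77.8% implies 7.4% above 12, against a true 9.4% (−2.0). With 15–23% missing and weak dependence the gap was under 0.5 point.

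**Would observed values for both rates be enough?** In the 26.3% row the observed ≥10 rate is 87.8%, so the difference is 87.8 − 75.4 = 12.4 points. That is a consistent description of subjects with data, but it is 1.9 points above the full-FAS share. Imputing both rates is the better main analysis.

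**The case against.** The case for leaving the plan alone is a fair one. The split is openly prespecified, the endpoint is descriptive, SAP 11 confirms that nothing is tested, and observed values are a defensible choice for an exploratory endpoint. No section plans to subtract the rates. High Hb is reported directly through the any-time >12 and >13 g/dL proportions, and target control also through the percentage of time in range. An error of 1 to 2 points is small beside a planned CI width of 9.5 points. All of this stands and limits the weight of the point. It does not supply the missing denominator, and the any-time proportions do not measure a Week 16–24 mean above 12.

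Several stronger readings are tempting but unsupported:

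- *The rates come from different populations.* Both are assigned to the FAS. What differs is who contributes and how missing Hb is handled.
- *Subjects without Week 16–24 Hb are dropped.* The SAP does not say so; counting them as non-responders also fits its text.
- *The 10–12 rate describes completers only.* One central Hb in the window is enough. SAP Table 5 schedules Week 16 at Day 7 × 16 + 1 = 113 and opens its window 14 days earlier, on Day 99, and early-termination assessments map to the closest scheduled visit. Subjects who stop within the window can contribute.
- *The two rates cannot be read together.* With little missing Hb, or missingness unrelated to Hb, and subjects with data as the denominator, the discrepancy is near zero.

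**Conclusion.** The point holds as one of comparability and possible bias, and it is minor. Two proportions from the same Week 16–24 mean use different missing-data rules, and one has no stated denominator.

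The size is conditional, because the documents give no missing rate. With 26–32% missing and dropout driven by Hb, the observed-value 10–12 rate is 1.3 to 1.8 points too high and the implied share above 12 g/dL 1.3 to 2.0 points too low. The direction assumes that subjects without data are less often in range than those with data. The unstated denominator matters more: about 55% under a non-responder rule against 74% for the full FAS in the simulation at 26% missing. Even with dropout unrelated to Hb, the two denominators give 74.1% and 55.6% at 25% missing.

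MI removes this bias only so far as missingness is explained by the Hb values in the imputation model. Confidence is high in the textual split and in the missing denominator, and limited in the size of the consequence. The ≥10 g/dL result is unaffected.

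**What to change.** 1. In SAP 9.2.2, derive the Week 16–24 mean 10–12 g/dL indicator in the same 200 imputed datasets and pool it with PROC MIANALYZE, as for ≥10 g/dL.
2. As a supplement, show observed-value versions of both rates, each with the number contributing and a stated denominator, and say how FAS subjects with no Week 16–24 Hb are counted.
3. Keep observed values for the any-time >12 and >13 g/dL proportions.
4. Give the 10–12 endpoint one label, secondary or exploratory, in both SAP Section 2 and SAP 4.2.

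The cost is a few lines of SAS on datasets the plan already creates, one supplementary table and a wording change. No new data are needed.
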